2 INTRODUCTION

The neonatal MHC-class-I-like FcRn recycles immunoglobulin and albumin from most cells and transports it bi-directionally across epithelial barriers to affect systemic and mucosal immunity. It was shown that FcRn rescues both IgG and albumin from intracellular lysosomal degradation by recycling it from the sorting endosome to the cell surface (Anderson et al, 2006). With respect to IgG, this is achieved by interaction of IgG with the receptor, FcRn. Thus, in effect FcRn salvages IgG, saving it from degradation and returning it to circulation. Albumin is similarly recycled by FcRn, though via a different binding site on the FcRn molecule. It has been shown that knockout or blockade of FcRn removes this recycling resulting in endosomal catabolism of IgG and a marked reduction of IgG concentrations in both the vascular and extravascular (tissue) compartments. In effect, blockade of FcRn accelerates removal of endogenous IgG and, if the albumin binding site is also blocked, potentially of albumin.

Immune thrombocytopenia is a clinical disorder in which thrombocytopenia manifests as a bleeding tendency, purpura, or petechiae. Autoantibodies against platelet antigens are considered to be a hallmark of ITP. Production of pathogenic IgG autoantibodies by plasma cells is accepted as the central underlying pathophysiological mechanism in a number of IgG-mediated autoimmune diseases, which includes ITP. In some patients, antibodies recognize antigens derived from a single glycoprotein, whereas in others, antibodies recognize multiple glycoproteins. The spleen is the key organ in the pathophysiology of ITP, not only because platelet autoantibodies are formed in the white pulp, but also because mononuclear macrophages

Based on the time from diagnosis, the first phase (up to 3 months) is the "newly-diagnosed ITP," phase 2 (>3 months up to 12 months) is the "persistent phase," and after 12 months the "phase" starts. These phases also reflect the line.

The major goal for treatment of ITP is to achieve a platelet count that prevents major bleeding rather than correcting the platelet count to normal levels. The management of ITP should be

tailored to the individual patient and it is rarely indicated in those with platelet counts above $50x10^9/L$ in the absence of bleeding, trauma, surgery, or high risk factors (eg, patients on anticoagulation therapy) (EMA/CHMP/153191/2013, 2014). However, there is general agreement that adults with a count of $<30x10^9/L$ with bleeding at diagnosis require treatment

The first line of treatment for newly-diagnosed ITP is generally agreed and based on the use of corticosteroids and intravenous immunoglobulin (IVIg). Patients who fail to respond or who relapse face the options of treatment with second line drug therapy or splenectomy but there is no clear evidence to support the best approach. Splenectomy can provide long-term efficacy in around 60% of cases and recent guidelines suggest considering a splenectomy after 12 months. Splenectomy is an invasive procedure associated with acute complications due to thrombocytopenia (like bleeding events) and long-term complications from loss of splenic functions. Asplenic subjects are at increased risk of life-threatening infections. Splenectomy may increase morbidity from venous thromboembolism or atherosclerosis (Ghanima et al. 2012). Second line drug therapies include high-dose dexamethasone or methylprednisolone; high-dose IVIg or anti-D Ig; vinca alkaloids; dapsone and danazol; the immunosuppressants cyclophosphamide, azathioprine, and cyclosporine; or mycophenolate mofetil and *Helicobacter pylori* eradication if applicable. The anti-CD20 monoclonal antibody rituximab - even if not licensed for the treatment of ITP - and the thrombopoietin-receptor (TPO-R) agonists are considered as second line as well as third line options.

Treatment-related morbidity is also a significant contributing factor; long-term courses of corticosteroids, other immunosuppressive medications, or splenectomy may be required to maintain a platelet count in a safe range in patients with chronic treatment-resistant ITP and morbidity and mortality can be related to treatment, reflecting the complications of therapy with corticosteroids or splenectomy. There thus remains a considerable unmet medical need for new therapeutic options in the treatment of ITP. UCB7665 may become the first targeted therapy to remove the autoantibodies to platelets providing a safe and tolerable alternative for patients with persistent or chronic ITP in acute or maintenance therapy.

UCB7665 is a humanized anti-FcRn monoclonal antibody that has been specifically designed to inhibit IgG binding to FcRn without inhibiting albumin binding to FcRn. UCB7665 is being developed as an inhibitor of FcRn activity with the aim to reduce the concentration of pathogenic IgG in patients with IgG autoantibody mediated diseases. UCB7665 was derived from a rat antibody with specificity for human FcRn by engineering the rat antibody into a humanized IgG4P format. The construct encoding UCB7665 was created by grafting the complementarity-determining region (CDRs) from the parental rat heavy and light chain variable regions onto a human IgG4P and kappa chain genetic background, respectively. The resulting UCB7665 contains only the original rat sequences that comprise the antigen binding site; all other sequences are human in origin.

UCB7665 is being evaluated in a study in healthy subjects (UP0018) with escalation of single intravenous (iv) and sc dosing. The outcomes are safety, tolerability, PK, and the PD effect on total IgG levels. Doses of UCB7665 1, 4, and 7mg/kg have been administered in 3 cohorts for the iv route and in 3 cohorts for the sc route. Preliminary information from the study is summarized below.

In the iv cohorts, the maximum tolerated dose was reached at UCB7665 4mg/kg. The most common TEAEs in all iv cohorts were mild to moderate gastrointestinal disturbances (nausea, vomiting, and diarrhea) and mild to severe headaches.

In the sc cohorts, a comparable tolerability profile was seen with UCB7665 7mg/kg sc and 4mg/kg iv. Adverse events of mild to moderate severity for headaches and gastrointestinal disturbances were observed. There were fewer cases of headache and gastrointestinal disturbances in the overall sc cohorts compared to overall iv cohorts.

In 4-week and 13-week toxicity studies with 8-week, treatment-free recovery periods in Cynomolgus monkeys, UCB7665 induced the expected large decreases (75% to 90%) in plasma IgG in all animals which was maintained for the duration of both studies in the majority of the animals, with only minor effects on albumin levels. UCB7665 was well tolerated at the highest dose levels tested of UCB7665 150mg/kg sc and UCB7665 150mg/kg iv administered every 3 days (there was no observed adverse effect level [NOAEL]).

Further information on the PK, PD, and safety profiles for UCB7665 from nonclinical studies, and preliminary safety information from clinical studies (including data from this study), can be obtained from the current version of the UCB7665 Investigator's Brochure.

Subjects will also have the option of providing additional informed consent for exploratory DNA and RNA (mRNA and miRNA) analyses as described in Section 5.1.1.

3 STUDY OBJECTIVE(S)

3.1 Primary objective

The primary objective of the study is:

 To evaluate the safety and tolerability of UCB7665 administered by sc infusion in subjects with ITP

3.2 Secondary objectives

The secondary objectives of this study are:

- To assess the clinical efficacy of UCB7665 as measured by the change in platelet count
- To assess the PD effect of UCB7665 as measured by the change in total IgG concentration in serum

3.3 Exploratory objectives

The exploratory objectives of this study are:

- To evaluate the clinical efficacy as measured by the change in ITP bleeding score
- To evaluate the effect of UCB7665 on the concentrations of total protein, albumin, α-globulin and β-globulin, IgG subclasses, IgM, IgA, and IgE, and serum and plasma complement levels
- To evaluate the emergence of ADA with respect to immunogenicity and PK/PD

- To evaluate the relationship between changes in platelet count and total IgG, IgG subclasses, ITP-specific autoantibodies
- To assess the plasma concentrations of UCB7665 administered by sc infusion
- To evaluate the genomic components of ITP to understand the molecular etiology, progression, and treatment of the disease, applicable only for subjects consenting to participate in the optional genomic analyses substudy.

4 STUDY VARIABLES

4.1 Primary variable

The primary safety variable is:

• Occurrence of TEAEs

4.2 Others and exploratory variables

4.2.1 Safety variables

The other safety variables are:

- Vital sign values and change from Baseline over time (systolic and diastolic blood pressure, temperature, pulse rate, respiratory rate, and body weight)
- 12-Lead ECG parameters and change from Baseline over time
- Laboratory values and change from Baseline over time (hematology including coagulation parameters, clinical chemistry, and urmalysis)
- Values and change from Baseline in concentrations of total protein, albumin, α -globulin, and β -globulin over time
- Change from Baseline in exploratory safety biomarkers over time
- TEAEs leading to withdrawal of IMP

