6.4 Withdrawal criteria

Subjects are free to withdraw from the study at any time, without prejudice to their continued care

Subjects should be withdrawn from the study if any of the following events occur:

- 1. Subject withdraws his/her consent.
- 2. Subject develops an illness or has a change in health status that would interfere with his/her continued participation, including but not limited to:
 - Subject has a serious infective episode requiring hospitalization or iv antibiotic therapy (including but not limited to bacteremia or sepsis, bacterial meningitis, osteomyelitis or septic arthritis, bacterial pneumonia, or visceral abscess).
 - Subject experiences a severe AE of gastrointestinal disturbance or headache which is considered related to the IMP in the opinion of the investigator.

- Subject has a severe infusion reaction requiring corticosteroid and/or epinephrine therapy.
- Subject has an anaphylactic reaction requiring corticosteroid and/or epinephrine therapy.
- Subject has a life threatening bleeding event.
- Subject has a TB test that is confirmed positive or any further evidence suggestive of potential TB infection (eg, close exposure) and further examinations result in a diagnosis of active TB or LTB. Refer to Section 12.8.1 for further details and instructions.
- If an NTMBI infection is identified during a study, the same withdrawal procedures as those used for an active TB infection identified during the study should be followed.
- 3. Subject requires rescue therapy (Section 7.8.3).
- 4. There is confirmation of a pregnancy during the study, as evidenced by a positive pregnancy test.
- 5. The sponsor or a regulatory agency requests withdrawal of the subject.

Subjects MAY be withdrawn from the study if any of the following events occur:

- 1. Subject is noncompliant with the study procedures or medications in the opinion of the investigator.
- 2. Subject takes prohibited concomitant medications as defined in this protocol that could compromise subject's safety.

Subjects MUST stop treatment with the IMP if the platelet count is >350x10⁹/L during the Dosing Period. Subjects should continue in the study and attend the protocol defined visits in the Observation Period.

Potential drug induced liver injury IMP discontinuation criteria 6.4.1

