7.2 Treatment to be administered

Subjects in Dose Arm 1 will receive 5 sc doses of UCB7665 4mg/kg at 1-week intervals.

Subjects in Dose Arm 2 will receive 3 sc doses of UCB7665 7mg/kg at 1-week intervals.

Subjects in Dose Arm 3 will receive 2 sc doses of UCB7665 10mg/kg at a 1-week interval.

Subjects in Dose Arm 4 will receive 1 sc dose of UCB7665 15mg/kg.

Subjects in Dose Arm 5 will receive 1 sc dose of UCB7665 20mg/kg.

The IMP will be administered as a sc infusion using an infusion pump:

The perfusor will be programmed at a constant flow rate of 20mL/h for all subjects. In the case of any blockage of the infusion, a suitable flush (eg, 0.9% sodium chloride) is allowed.

The subject's body weight at Screening Visit will be used for the dose calculation. The dose will be constant for a subject throughout the duration of the study, and will not be adjusted during the treatment.

The exact procedure for dose preparation according to dose arm and body weight will be provided in a pharmacy manual.

The infusion rate may be reduced at any time at the discretion of the investigator. If an infusion is interrupted, it can be restarted if the investigator considers it appropriate to do so. The chronology of these events should be recorded accurately in the source data and eCRF.

In the event of a severe infusion reaction, the subject must permanently discontinue IMP (see Section 12.1.10).

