14.3.2 Other safety analyses

The absolute and relative frequencies for subjects with a given TEAE with respect to the preferred term according to the latest available version of the MedDRA, as well as the absolute frequencies of the individual TEAEs that have occurred, will be determined within each system organ class. Additional tables will summarize TEAEs by maximum intensity and causal relationship with UCB7665, as judged by the investigator. Adverse events will be categorized by severity according to the CTCAE version 4.03 grading. In case the CTCAE grading is not available, the intensity (mild/moderate/severe) will be utilized. For the purpose of the tabulations CTCAE grades will be aligned with the intensity classifications (mild/moderate/severe) to enable pooling of the AEs in the summaries. The TEAEs leading to discontinuation of IMP and treatment-emergent SAEs will also be summarized. The action taken, time of onset relative to dosing, and duration of each AE will be listed only.

For the continuous laboratory variables, the values and changes from Baseline will be summarized at each time point. For categorized values according to the reference range, shift tables from Baseline to each post-Baseline time point will be presented for selected variables to be defined in the SAP. Values outside the reference range will be flagged in the data listings. The number and percentage of subjects with markedly abnormal laboratory results (based on CTCAE grading) will be tabulated for each dose arm.

Normal versus abnormal findings with regard to the various ECG parameters and the overall ECG will be analyzed as required. The focus of the 12-lead ECG analysis will be the identification of outliers and of any trends for changes following administration of UCB7665 with respect to QT/QTc. Descriptive statistics will be presented for ECG value and changes from Baseline over time based on the mean of the triplicate assessments at each time point.

Descriptive statistics will be reported for all vital sign measurements (including systolic and diastolic blood pressure, pulse rate, temperature, and respiratory rate). Measured values and changes from Baseline will be summarized by time point.

Physical examination findings and the results of any pregnancy testing will be presented in listings only.

Safety analyses will be presented by dose arm.

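### The by-arm count of TEAEs that end treatment misses every event after the last planned infusion, so comparing arms on this one variable is confounded with the number of infusions

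*Protocol*

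**What the plan says.** Section 4.2.1 lists "TEAEs leading to withdrawal of IMP" as one of the safety variables other than the primary one. Section 14.3.2 says "The TEAEs leading to discontinuation of IMP and treatment-emergent SAEs will also be summarized" and adds "Safety analyses will be presented by dose arm". The two sections use different words (withdrawal, discontinuation) for what reads as the same variable. Neither limits it to arms or subjects with a dose still to come.

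Section 7.2 fixes the number of infusions. At one end, "Subjects in Dose Arm 1 will receive 5 sc doses of UCB7665 4mg/kg at 1-week intervals". Next, "Subjects in Dose Arm 2 will receive 3 sc doses of UCB7665 7mg/kg at 1-week intervals". Arm 3 has two infusions of 10mg/kg and Arm 4 has one of 15mg/kg. At the other end, "Subjects in Dose Arm 5 will receive 1 sc dose of UCB7665 20mg/kg". Section 12.1.1 counts TEAEs from the first administration to 8 weeks after the final dose, in every arm.

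**The concern.** For a TEAE to lead to withdrawal of IMP, there must be IMP left to withdraw. In Arms 4 and 5 that holds only while the single infusion is running. In Arms 1 to 3 it holds until the last infusion, and then fails there too. How much of the safety follow-up can produce a countable event therefore depends on how many infusions were planned.

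That matters because the number of infusions is what the regimens vary. Section 5.4.5 explains that Arms 3 and 5 give the same cumulative dose in fewer, larger infusions, with Arm 4 as a bridge, and the primary objective is safety and tolerability. A table of events that ended treatment is a natural place to look for tolerability. Here it would show a count near zero by construction in the two arms with the largest single dose, with nothing to warn the reader.

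**Working it through.** **Inputs.** Infusions per arm, k = 5, 3, 2, 1, 1 (Section 7.2). Dose per infusion = 4, 7, 10, 15, 20mg/kg (same section). Arm sizes 15, 15 and then 6 to 12 in each of Arms 3 to 5 (Section 5.1). No rate for treatment-ending TEAEs is given, so p, the chance of such a TEAE after any one infusion, is assumed and varied.

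**Check against the plan's own figures.** Dose times infusions is 4×5, 7×3, 10×2, 15×1, 20×1 = 20, 21, 20, 15, 20mg/kg, which matches the Summary. Arm sizes add to 48 to 66, also as stated. Arms 4 and 5 hold 12 of 48 (25%) to 24 of 66 (36%) of the planned subjects.

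**Formulas.** After the first infusion, k−1 infusions remain: 4, 2, 1, 0, 0. The risk of a treatment-ending TEAE after any infusion is 1−(1−p)^k. The part that the variable can count is 1−(1−p)^(k−1), because an event after the last infusion has nothing left to cancel. Permanent stops of a running infusion are outside this sum; they can count in every arm.

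**Equal risk, p = 5% per infusion in every arm**

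| Arm | True | Countable | Lost, points | Lost, share of true |
|---|---|---|---|---|
| 1 | 1−0.95^5 = 22.6% | 1−0.95^4 = 18.5% | 4.1 | 18% |
| 2 | 1−0.95^3 = 14.3% | 1−0.95^2 = 9.8% | 4.5 | 32% |
| 3 | 1−0.95^2 = 9.8% | 5.0% | 4.8 | 49% |
| 4 | 5.0% | 0% | 5.0 | 100% |
| 5 | 5.0% | 0% | 5.0 | 100% |

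The absolute loss is nearly constant at 4 to 5 points; the relative loss runs from 18% to 100%. At other values of p the countable risk is 7.8/4.0/2.0/0/0% (p = 2%) and 34.4/19.0/10.0/0/0% (p = 10%).

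**Risk proportional to dose, assumed 1% per mg/kg (p = 4, 7, 10, 15, 20%)**

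| Arm | True | Countable |
|---|---|---|
| 1 | 1−0.96^5 = 18.5% | 1−0.96^4 = 15.1% |
| 2 | 1−0.93^3 = 19.6% | 1−0.93^2 = 13.5% |
| 3 | 1−0.90^2 = 19.0% | 10.0% |
| 4 | 15.0% | 0% |
| 5 | 20.0% | 0% |

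Arm 5 has the highest true risk and, with Arm 4, the lowest countable risk. At 2% per mg/kg the pattern is the same: 34.1/36.4/36.0/30.0/40.0% true against 28.4/26.0/20.0/0/0% countable.

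**The case against.** The best defence is that this is one descriptive count among several, and the others still see these events. The primary variable is the occurrence of TEAEs, followed for 8 weeks after the final dose in every arm. Section 14.3.1 also splits it by Dosing and Observation Period. Section 14.3.2 adds maximum intensity, causality and SAEs, Section 12.4 requires immediate reporting of severe headache and moderate to severe GI events, and Section 14.4.5.1 tabulates reasons for leaving the study. Nothing in the protocol ties dose escalation to IMP-withdrawal counts. All of this stands, and it limits the harm to one variable.

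Four stronger readings are tempting, and the documents do not support them.

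- A reader might infer that the highest doses will look best tolerated overall. Only this variable is blocked; a severe related headache on Day 2 in Arm 5 still appears as a severe, related TEAE.
- A reader might infer that the event is impossible in Arms 4 and 5. Permanently stopping the running infusion still counts, and Sections 7.2 and 12.1.10 require permanent discontinuation after a severe infusion reaction.
- A reader might take the whole fall from 18.5% to 0% as artefact. Under equal risk per infusion most of it is real: arms with more infusions have more chances of an event, and true risk falls from 22.6% to 5%.
- A reader might treat "Subject experiences a severe AE of gastrointestinal disturbance or headache which is considered related to the IMP" as an IMP-stopping rule that works only in multi-dose arms. Section 6.4 lists it as a reason for withdrawal from the study, with no time limit, so it can apply in every arm.

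It can also be said that denominators belong in the SAP. The protocol, however, itself names the variable and sets the by-arm display, so the restriction belongs beside them.

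**Conclusion.** The point holds for this one variable. A TEAE arising after the last planned infusion cannot be captured. All post-infusion events are lost in Arms 4 and 5, and a smaller share in Arms 3, 2 and 1, so the by-arm comparison is confounded with the number of infusions. With an assumed equal 5% risk per infusion the relative loss is about 18%, 32%, 49%, 100% and 100%. Whether the display merely understates or actually reverses the ordering depends on how risk changes with dose, which the documents do not say; under the assumed proportional increase it reverses.

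The figures rest on the assumed p, on the period after the last infusion carrying the same risk as the period after any other, and on leaving out stops during an infusion. The structural part, 4, 2, 1, 0 and 0 infusions remaining after the first, needs no assumption. It is worth correcting because a structural zero could be read as tolerability, but it does not undermine the safety assessment as a whole.

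**What to change.** In Sections 4.2.1 and 14.3.2:

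1. Report TEAEs leading to withdrawal of IMP with a denominator of subjects who had an infusion remaining, marked not applicable for Arms 4 and 5. Show permanent stops of a running infusion on a separate line for all arms.
2. Add, for all arms, the number of subjects with a TEAE that meets an existing IMP-stopping or withdrawal criterion of the protocol (Sections 6.4, 6.4.1, 7.2 and 12.1.10), whether or not a further infusion was planned.

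The first item removes the misleading zeros. The second also deals with the partial loss in Arms 1 to 3, which the denominator alone does not. Slowing or brief interruption of an infusion is best kept out of the second count, since Section 7.2 leaves rate changes to the investigator's discretion.

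The cost is one derived flag and one table. AE severity and causality are already recorded, and for infusion changes Section 7.2 requires that "The chronology of these events should be recorded accurately in the source data and eCRF". No dose, stopping rule or study procedure changes.

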4.2.2 Efficacy variables

The efficacy variables are:

- Response during the study: platelet count $\ge 30 \times 10^9 / L$ and at least 2-fold increase of the Baseline count
- Complete Response during the study: platelet count $\geq 100 \times 10^9 / L$

Platelet count $\geq 50 \times 10^9 / L$ during the study

- Response by visit
- Complete Response by visit
- Platelet count $\geq 50 \times 10^9 / L$ by visit

- The maximum value and maximum increase from Baseline in platelet count during the study
- Value and change from Baseline in platelet count over time
- Baseline-corrected AUEC for platelet count
- Time to Response: time from starting treatment to achievement of Response
- Time to Complete Response: time from starting treatment to achievement of Complete Response
- Time to achieving platelet count $\geq 50 \times 10^9 / L$
- Duration of Response: measured from achievement of Response to loss of Response (loss of Response defined as platelet count below $30x10^9/L$ or less than 2-fold increase of Baseline platelet count)
- Duration of Complete Response: measured from achievement of Complete Response to loss of Complete Response (loss of Complete Response defined as platelet count below $100 \times 10^9 / L$)
- Duration of platelet count $>50 \times 10^9$ /L: measured from achievement of platelet count $\geq 50 \times 10^9 / L$ to reduction of platelet count below $50 \times 10^9 / L$
- Clinical Response: platelet count $\ge 30 \times 10^9 / L$ and at least 2-fold increase from Baseline value and absence of bleeding
- Time to Clinical Response: time from starting treatment to achievement of Clinical Response
- Duration of Clinical Response: measured from achievement of Clinical Response to loss of Clinical Response (loss of Clinical Response defined as platelet count <30x10⁹/L or less than 2-fold increase from Baseline platelet count or presence of bleeding)
- Complete Clinical Response: platelet count $\geq 100 \times 10^9 / L$ and absence of bleeding
- Time to Complete Clinical Response: time from starting treatment to achievement of Complete Clinical Response
- Duration of Complete Clinical Response: measured from achievement of Complete Clinical Response to loss of Complete Clinical Response (loss of Complete Clinical Response defined as platelet count $<100 \times 10^9$ /L or presence of bleeding)
- No Clinical Response: platelet count <30x10⁹/L or less than 2-fold increase from Baseline or presence of bleeding
- ITP bleeding score over time
- Value and change from Baseline in NFI-MS summary score over time

Pharmacokinetic variable The PK variable is:

Plasma concentration of UCB7665 over time

15 Feb 2017

TP0001

